SBRT	Stereotactic Body Radiation Therapy
SHIM	Sexual Health Inventory Men
SIB	Simultaneous integrated boost
STAMPEDE	Radiotherapy to the primary tumour for newly diagnosed, metastatic prostate cancer
SUSAR	Suspected Unexpected Serious Adverse Reaction
TRUS	Transrectal Ultrasound
UAP	Unanticipated Problem
WCMC	Weill Cornell Medical College

Summary of changes for version 5.0 dated 26JUL2023

Sections	Change	Rationale
Principal Investigator section	Changing Principal investigator from [name] to [name]	Changing Principal investigator from [name] to [name], since [name] will no longer be at WCM.
No changes to the Informed consent since the study is closed to accrual and only in follow up.		

Summary of changes for version 4.0 dated 03FEB2022

Sections	Change	Rationale
Primary Objective	Revising the toxicity measurement timeframe stated in the primary objective from 30 days to 3-6 months post treatment.	Revising the toxicity measurement timeframe stated in the primary objective from 30 days to 3-6 months post treatment and keep it consistent with the study calendar.
Personnel changes	Adding [name] to the protocol cover page.	Updating personnel and contact information. Admin amendment approved on 16NOV2021.
No changes to the Informed consent		

Summary of changes for version 3.0 dated 05OCT2021

Sections	Change	Rationale
Principal Investigator section	Changing Principal investigator from [name] to [name]	Changing Principal investigator from [name] to [name]
Personnel changes	Removed [name] as Nurse practitioner and [name] as study coordinator, Added [name]. Updated contact details for personnel.	Change of personnel and contact information.
Informed consent changes		
Principal Investigator section	Changing Principal investigator from [name] to [name]	Changing Principal investigator from [name] to [name]

Summary of changes for version 2.0 dated 24JAN2020.

1. **Inclusion Criteria:** Must have metastatic prostate cancer proven on biopsy or imaging
2. **Exclusion Criteria:** Removing criteria # 4 - Evidence of disease progression on bone scan, MR and/or CT
3. Revised accrual ceiling to 25 patients as stated in the IRB application
4. Adding [name] as data manager to the protocol to keep it consistent with the IRB personnel list.
5. Updating QOL – AUA to I-PSS
6. Study Calendar – clarifying that blood/stool collection is optional at all time points as stated in the informed consent.

Informed consent changes:

1. The protocol version date is incorrect - changing the footer of the informed consent.
2. Making study calendar consistent with the protocol.

Document History

Document Name	Version number	Version Date
Amendment 4	5.0	26JUL2023
Amendment 3	4.0	03FEB2022
Amendment 2	3.0	05OCT2021
Amendment 1	2.0	24JAN2020
Initial Protocol	1.0	23JUL2019

Protocol Summary

PRAGMA (Prostate Radio Ablation Guided by Magnetic resonance imaging Acquisition) in metastatic prostate cancer

IRB Protocol #: 19-04020263

Short Title:	MRI-guided prostate SBRT for metastatic prostate cancer
Principal Investigator:	[name]
Sample Size:	N = 20
Accrual Ceiling:	This study plans to enroll a total of 25 patients
Study Population:	Patients with metastatic prostate cancer
Accrual Period:	2 years
Study Design:	Single-arm study for safety

Study Intervention Description:

MR-guided Prostate SBRT:

Prostate SBRT has become a standard of care for the treatment of localized prostate cancer. Radiation is delivered to the prostate and seminal vesicles in 5 treatment sessions (fractions). Doses ranging from 35-45 Gy in 5 fractions have demonstrated good outcomes with acceptable toxicity when planning is delivered appropriately.

There is emerging evidence that patients with *non*-localized prostate cancer also derive benefit from radiation (RT) to the primary tumor. The STAMPEDE multiarm British trial recently reported that patients with low burden metastatic prostate cancer have an overall survival benefit from prostate RT. Doses of radiation used in the STAMPEDE trial were either 36 Gy in 6 fractions, or 55 Gy in 20 fractions.

The MRidian ViewRay offers delivery of prostate SBRT with real-time MR guidance, which provides superior soft-tissue differentiation with excellent visualization of the prostate. This ViewRay platform offers the ideal setting for this study, that aims at precisely delivering prostate SBRT with a simultaneous integrated boost (when indicated) to visible nodules.

In this study, we hope to demonstrate the safety of using 36.25 Gy in 5 fractions, plus a simultaneous integrated boost (when indicated), in patients with metastatic prostate cancer.

Hypothesis: Patients with metastatic prostate cancer can undergo MRI-guided prostate SBRT without significant adverse events, similar to what has been reported for patients with localized prostate cancer.

We hypothesize that prostate SBRT will be well-tolerated in metastatic prostate cancer patients, with quality of life outcomes similar to what has been reported in non-metastatic prostate cancer patients.

We also hypothesize that prostate SBRT will impact lymphocyte counts and neutrophil

lymphocyte ratio, as well as the diversity, abundance and composition of the gut microbiome, when baseline datapoints are compared to post-RT and follow up datapoints.

Primary objective: To assess safety of delivering MRI-guided prostate SBRT in patients with metastatic prostate cancer.

Treatment will be deemed safe if there is no more than 3 acute >G3 likely radiation treatment related GI/GU toxicity within 3-6 months after treatment (CTCAE 5.0 criteria) completion. Given that the treatment plans will meet rigorous normal tissue constraints used for standard prostate SBRT that have been established now with up to 10 year follow up data in patients with localized prostate cancer, we do not anticipate any increased toxicity on this study for metastatic prostate cancer patients.

Secondary objective: To obtain quality of life and toxicity data after prostate SBRT.

We will measure quality of life (HRQOL) using: 1) the Expanded Prostate Cancer Index Composite (EPIC-26) short form questionnaire, 2) International Prostate Symptom Score (I-PSS). QOL assessments will occur at baseline, 3-6 months, and at 9-12 months.

Toxicity data will be measured with CTCAE 5.0 at 3-6 months, and at 9-12 months.

Correlative study objectives:

1. To explore gut microbiome changes associated with prostate radiation
2. To collect complete blood count (CBC) measurements at baseline, post-treatment and 3-6 month followup to assess impact of SBRT on immune correlates and neutrophil lymphocyte ratios.

SCHEMA

[figure not shown]

TABLE OF CONTENTS

SCHEMA.....	11
1 STUDY OBJECTIVES	14
1.1 PRIMARY OBJECTIVES	14
1.2 SECONDARY OBJECTIVES	14
1.3 CORRELATIVE STUDY OBJECTIVES.....	14
2 BACKGROUND	15
2.1 RADIATION TO THE PROSTATE: RATIONALE FOR TREATING PATIENTS WITH METASTATIC PROSTATE CANCER	15
2.2 PROSTATE CANCER RADIOTHERAPY: RATIONALE FOR EXTREME HYPOFRACTIONATION SBRT	16
2.3 BIOLOGICAL RATIONALE FOR SBRT	16
2.4 SBRT OUTCOMES.....	17
2.5 RATIONALE FOR SIMULTANEOUS INTEGRATED BOOST.....	18
2.6 NEED FOR IGRT IN PROSTATE RADIOTHERAPY.....	18
2.7 VIEWRAY: A UNIQUE RADIATION DELIVERY APPROACH	19
2.8 RATIONALE FOR CORRELATIVE STUDIES BACKGROUND: MICROBIOME AND BLOOD SAMPLE COLLECTION	20

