The goal of this study is to assess safety of treating patients with metastatic prostate cancer with MRI-guided prostate SBRT. Safety is defined as lack of more than 3 patients with treatment related acute >G3 GI or GU toxicity within 3- 6 months post treatment. The proposed SBRT dose (36.25 Gy in 5 fractions to the whole prostate) has been reported in the literature to be safe and well tolerated (Table 2), with no acute G3 toxicity. The proposed boost dose to 40 Gy in applicable patients is within the range of current standard of care SBRT doses, and is also expected to be well-tolerated. Furthermore, it has been tested in our currently ongoing investigator initiated protocol in patients with non-metastatic prostate cancer (“MRI-guided Stereotactic Body Radiotherapy (SBRT) with Simultaneous Integrated Boost for Prostate Cancer” PI: [name], [name] IRB Protocol # 1802019010). As of 4/29/19, 15 patients with localized prostate cancer have enrolled on this study with planned accrual of 30 patients, and have demonstrated excellent safety and feasibility with boost doses up to 45 Gy. It

is therefore expected that similar outcomes can be achieved in patients with metastatic prostate cancer, though it is possible that the addition of systemic therapy may alter likelihood of toxicity.

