12.1.1 Primary Objectives

Safety of this approach will be determined by assessing acute GI/GU toxicity (CTCAE 5). The treatment will be deemed safe if no more than 3 patients experience a grade 4 likely radiation treatment related GI/GU (or higher) adverse event within 3-6 months from the end of treatment.

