12.1.3 Correlative Study Objectives

Microbiome and labs will be collected for exploratory analyses to see how radiation impacts the host microbiome and peripheral immune correlates found in blood.

12.2 *Sample Size/Accrual Rate*

We plan to accrue 20 patients over 2 years, or about 4-6 patients every 6 months.

12.3 *Analysis of Primary and Secondary Endpoints*

Primary Endpoint:

The treatment will be deemed safe if the grade 4+ likely radiation treatment related GI/GU adverse event rate is less than 10% within 3-6 months of the end of treatment. The proportion of patients that experience a >grade 3 GU/GU adverse event will be determined with a binomial

point estimate and corresponding exact 95% binomial confidence interval. If the lower bound of the interval is below 10%, the treatment will be considered safe.

Secondary Endpoints:

QOL measures at baseline and at follow up (3-6 months post treatment start, and 9-12 months) will be summarized numerically and graphically using mean (sd), median (interquartile range), or count (percent) as appropriate, and 95% confidence intervals estimated where possible. The QOL value will be plotted over time with a line for each patient and a smoothed curve superimposed on the plot. Changes in scoring from pre- to post-treatment will also be determined. EPIC-26 overall scores as well as domain summary scores (urinary incontinence, urinary irritative/obstructive, bowel, sexual, hormonal) and individual item responses will be evaluated. Similarly, overall score as well as individual item responses will be assessed for the I-PSS survey.

Toxicity will be assessed using CTCAE 5.0 criteria at 3-6 months and 9-12 months.

These analyses will be descriptive.

Correlative study endpoints:

Microbiome

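### The primary safety criterion contradicts itself at any permitted sample size: a limit of three patients allows 15% of 20 or 12% of 25, Section 12.3 requires a rate below 10%, and a third rule passes up to 25%

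*Combined protocol and SAP*

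**What the plan says.** Three rules for calling the treatment safe stand in the current text.

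- **Count rule.** Section 12.1.1 has the treatment "deemed safe if no more than 3 patients experience a grade 4 likely radiation treatment related GI/GU (or higher) adverse event". Section 2.7 agrees: "Safety is defined as lack of more than 3 patients with treatment related acute >G3 GI or GU toxicity". The primary objective in the Protocol Summary, Section 1.1 and Section 10 use the same limit of three, but count toxicities or events rather than patients. None of these places gives a denominator.
- **Rate rule.** Section 12.3 (Primary Endpoint) calls the treatment safe if the grade 4+ "adverse event rate is less than 10% within 3-6 months of the end of treatment".
- **Confidence-limit rule.** The same paragraph specifies an exact 95% binomial interval and adds: "If the lower bound of the interval is below 10%, the treatment will be considered safe".

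On size, the Protocol Summary lists N = 20 and, in the next row, an accrual ceiling worded as "This study plans to enroll a total of 25 patients". Section 12.2 says "We plan to accrue 20 patients over 2 years, or about 4-6 patients every 6 months". No text says what the five extra places are for, or whether the primary endpoint is divided by enrolled, treated or evaluable patients.

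**The concern.** Each rule is written as the definition of safe, and nothing says which one governs. They do not agree. With three affected patients the count rule passes the treatment although the observed rate is above the 10% in Section 12.3. With four or five of 20, the count rule fails it and the confidence-limit rule passes it.

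The confidence-limit rule also works in a weak direction. A lower limit below 10% shows only that the data do not rule out rates under 10%. It does not show that the rate is under 10%.

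Safety is the study's primary endpoint and there is no comparator arm. If a handful of events occur, the headline conclusion would depend on which sentence the analyst cites.

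**Working it through.** **Inputs.** N = 20 (Protocol Summary, 12.2); ceiling 25 (Protocol Summary); limit of 3 (12.1.1, 2.7 and elsewhere); rate below 10%, taken as strict (12.3); lower limit of an exact two-sided 95% interval below 10% (12.3). Each event is treated as one patient.

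**The plan's own figure.** N = 20 cannot be reproduced: the documents give no error rate, power, assumed event rate or target precision.

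**Step 1: the count limit as a proportion.** 3/20 = 15.0%; 3/25 = 12.0%. For 3/n to be below 10%, n must exceed 30: 3/30 = 10.0% and 3/31 = 9.7%. No size up to the ceiling of 25 reconciles the two rules.

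**Step 2: the three rules side by side.** The exact (Clopper-Pearson) lower limit for x of n is the 2.5% quantile of Beta(x, n − x + 1).

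| Affected | N = 20: observed (lower limit) | Count / rate / limit rule | N = 25: observed (lower limit) | Count / rate / limit rule |
|---|---|---|---|---|
| 1 | 5.0% (0.1%) | pass / pass / pass | 4.0% (0.1%) | pass / pass / pass |
| 2 | 10.0% (1.2%) | pass / **fail** / pass | 8.0% (1.0%) | pass / pass / pass |
| 3 | 15.0% (3.2%) | pass / **fail** / pass | 12.0% (2.5%) | pass / **fail** / pass |
| 4 | 20.0% (5.7%) | fail / fail / **pass** | 16.0% (4.5%) | fail / fail / **pass** |
| 5 | 25.0% (8.7%) | fail / fail / **pass** | 20.0% (6.8%) | fail / fail / **pass** |
| 6 | 30.0% (11.9%) | fail / fail / fail | 24.0% (9.4%) | fail / fail / **pass** |
| 7 | 35.0% (15.4%) | fail / fail / fail | 28.0% (12.1%) | fail / fail / fail |

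The rate column applies the 10% limit to the observed proportion. The rules disagree for 2 to 5 affected of 20, and for 3 to 6 of 25. The choice between 20 and 25 changes the rate rule only at two affected patients. It changes the confidence-limit rule only at six.

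**Step 3: probability of declaring safety.** For a rule that passes up to c patients, this is P(X ≤ c) with X ~ Binomial(N, p). Example for the count rule, N = 20, p = 0.10: 0.1216 + 0.2702 + 0.2852 + 0.1901 = 0.867.

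| Rule | Passes up to (N = 20; 25) | True rate 10% (N = 20; 25) | True rate 20% (N = 20; 25) |
|---|---|---|---|
| Count | 3; 3 | 0.867; 0.764 | 0.411; 0.234 |
| Observed rate below 10% | 1; 2 | 0.392; 0.537 | 0.069; 0.098 |
| Lower limit below 10% | 5; 6 | 0.989; 0.991 | 0.804; 0.780 |

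The true rates of 10% and 20% are chosen for illustration: the stated limit and twice that limit.

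**The case against.** The strongest reply is that 20 is the target and 25 only a cap. The two numbers stand in separate rows, Section 12.2 plans 20, and the version 2.0 change summary describes the 25 as a ceiling: "Revised accrual ceiling to 25 patients as stated in the IRB application". That is a fair reading, and a cap above a target is ordinary. What stands against it is narrow: the ceiling is worded as a plan to enrol 25, and no denominator is named.

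A reader might infer more than the documents support:

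- *That having two sizes causes the conflict.* It does not. Three patients against 10% conflicts at 20, at 25 and at every size up to 30.
- *That two affected patients fail at 20 and pass at 25.* This holds only when the 10% limit is applied to the observed proportion. Under the count rule and the confidence-limit rule, two patients pass at both sizes.
- *That a failing 2/20 could be rescued by enrolling five more event-free patients.* The version 5.0 change summary says the study is closed to accrual and in follow-up only, so this is no longer a live risk.
- *That the plan guards against a true rate of 15% or 12%.* Those are the highest observed proportions that the count rule lets through. They are not true rates that it controls.

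One could add that Section 13.2 suspends accrual for review once more than two patients have a related grade 4 event. That governs accrual. It does not settle which rule decides the primary endpoint.

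**Conclusion.** The concern holds as a contradiction among three stated criteria for the primary endpoint, at either sample size. The count rule allows an observed 15.0% of 20 or 12.0% of 25 against a stated limit of 10%. At a true rate of 20%, twice that limit, it would still declare safety with probability 0.411 (N = 20) or 0.234 (N = 25). The confidence-limit rule is looser again, passing observed rates up to 25% (5/20) or 24% (6/25).

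The missing denominator is a secondary defect. For the 10% limit read as an observed proportion, it decides the result only at two affected patients.

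The probabilities assume independent patients with a common event rate and one event per patient. The proportions in Steps 1 and 2 need no assumed event rate. The contradiction should be resolved before the primary analysis.

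**What to change.** 1. Name one denominator for the primary endpoint, for example all patients who started SBRT, using the actual number now that accrual is closed. Count patients rather than events throughout.
2. Delete the lower-limit sentence in 12.3 and keep the exact interval as a description of precision. Replacing it with an upper limit below 10% would not work: even with no events the exact upper limit is 16.8% at N = 20 and 13.7% at N = 25.
3. Use one criterion in the Protocol Summary, 1.1, 2.7, 10, 12.1.1 and 12.3. Either:
   - keep the limit of three, replace the 10% claim with the observed rate it allows (15% of 20, 12% of 25), and report the count rule's probabilities from Step 3; or
   - keep below 10% as an observed rate and state the matching count: at most 1 of 20, or at most 2 of 21 to 25 (2/21 = 9.5%; 3/25 = 12.0%).
4. Make and date the change before outcomes are examined. If they have already been seen, report the verdict under every stated criterion.

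**Cost.** The edits are to text, but they settle the primary success criterion after accrual has closed, so the reason and date should be recorded. The first option makes the stated tolerated rate less favourable. The second is stricter. The documents give no expected grade 4+ rate; at assumed true rates of 1%, 3% and 5% the second option would pass with probability 0.983, 0.880 and 0.736 at N = 20, and 0.998, 0.962 and 0.873 at N = 25.

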1 STUDY OBJECTIVES

HYPOTHESIS 1: Patients with metastatic prostate cancer can undergo MRI-guided prostate SBRT w/SIB without significant adverse events, similar to what has been reported for patients with localized prostate cancer using CTCAE criteria.

HYPOTHESIS 2: Patients with metastatic prostate cancer who undergo MRI-guided prostate SBRT will report good overall quality of life, similar to what has been reported for patients with localized prostate cancer. This will be measured using EPIC-26, I-PSS questionnaires, which are validated instruments that have been used to report QOL outcomes after prostate RT.

HYPOTHESIS 3: Patients may experience decline in neutrophil:lymphocyte ratios during radiation therapy, that is most prominent at end of treatment, but recovers to baseline by follow up. There will be alterations in the composition, diversity and abundance of microflora during radiation therapy when the microbiome is compared at baseline, to post-treatment, to follow up.

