1.3 Correlative Study Objectives

1.31

To collect complete blood count (CBC) measurements at baseline, post-treatment and 3-6 month followup to assess impact of SBRT on immune correlates and neutrophil lymphocyte ratios.

To describe gut microbiome changes (abundance, composition, diversity) associated with prostate radiation.

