9 CORRELATIVE/SPECIAL STUDIES

9.1 Correlative Study: Blood draws for immune correlates and microbiome collection

Patients will provide blood draw prior to, at the completion of radiation and at 3-6 months post treatment follow up. They will also be providing a stool sample for microbiome analysis at baseline, end of completion and 3-6 month follow up (last stool sample is optional). This is a correlative study.

Blood Sample Collection and Procedure

Blood samples (40-ml) will be collected in heparinized “Green Top” tubes (for PBMC and plasma isolation) and processed within 4 h of sample receipt. The PBMC will be isolated using a 1.077 g/ml Ficoll layer to enrich the leukocytes and remove the dead cells and any red cells, and cryopreserved in 10% DMSO, 90% human AB serum at 10×10^6

cells/vial and stored in liquid nitrogen for batch analysis. Plasma will also be aliquoted and stored at -80°C for batch analysis. We anticipate analyses of T cell subsets and neutrophil/lymphocyte ratios, as well as cytokine measurement and proliferation analyses (all markers of peripheral immune correlates to assess status over time).

Microbiome collection

Collection of Specimen(s): Patients will be provided with a stool collection container and be instructed on providing a specimen appropriately, which can be done from home or in the clinic.

Handling of Specimens(s): Samples received will be promptly frozen at 20 degrees C, and transferred within the next week to a -80 degree freezer or liquid nitrogen for long-term storage. DNA extractions and 16sRNA analysis will be performed once all samples are collected.

The microbial DNA will be isolated and used to provide DNA sequence information. We will perform taxonomic characterization of bacteria (using 16S rRNA). Prokaryotic diversity will be screened using massively parallel DNA sequencing, exploiting a multiplexing technique to generate 16S rRNA sequence tags, followed by analyses (statistical, clustering, and phylogenetic) to estimate the distribution of phylotypes, differential abundance, and the relative contributions between phylotypes and community dissimilarities to the overall diversity in individuals.

We will examine whether there are metagenome sequence content changes during radiation treatment, and study whether differences in gene content indicate differences in functional pathways between the normal and irradiated microbiome using pathway analysis.

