Statistical analysis of microbiome and metagenome composition will be performed in the R statistical programming environment using package *phyloseq*, which incorporates and builds upon community ecology packages such as *ade4* and *vegan* and employs the flexible graphic system *ggplot2*, to easily visualize complex data relationships. For 16S data, we will evaluate the adequacy of sequencing efforts using rarefaction plots. Alpha diversity index for each will be characterized through dominance, equitability, richness, evenness. The diversity metrics will be calculated at OTU and higher taxonomical levels to best characterize the community structure. We will test for associations of each of these alpha diversity metrics with the time relative to radiation exposure, using one-way ANOVA after even-sampling the observations to a depth cut-off maximizing the number of samples and depth. In addition, rank-abundance plots will be used to visualize differences in abundance of dominant taxa in the clinical and phenotypic groups. We will utilize skyline plots to visualize the patterns of community structure in terms of relative abundances in the collected samples between before and after the radiation treatment. Similarly, for metagenomic data, skyline plots will be used to reveal functional compositions of the samples. Heat-maps will be plotted to visualize clustering patterns in the data.

We will study the evolution of microbiome over time as a consequence of the radiation treatment. The relative abundances at each taxonomical level will be first normalized by log-ratio transformation. Then the transformed relative abundance of each individual taxa at multiple time points will be fitted by the linear mixed model along with the time effect and all subject-specific characteristics as the independent covariates. For the nonlinear trend, we will combine the nature splines with linear mixed model in the data analysis. The same model will be applied on the indices calculated in the ecology microbial analysis.

CBC collection

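### Section 12.3 specifies no community-level test of the composition part of Hypothesis 3, and its one-taxon-at-a-time models have no multiplicity rule

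*Combined protocol and SAP*

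**What the plan says.** Hypothesis 3 (Section 1) makes a three-part prediction, comparing baseline, post-treatment and follow-up samples: "There will be alterations in the composition, diversity and abundance of microflora during radiation therapy". The correlative objective in Section 1.3 is worded more softly, "To describe gut microbiome changes (abundance, composition, diversity) associated with prostate radiation", and Section 12.1.3 places the work in an exploratory tier: "Microbiome and labs will be collected for exploratory analyses".

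The microbiome part of Section 12.3 treats the three components as follows.

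- **Diversity:** one-way ANOVA of alpha-diversity metrics against time. The mixed model described below is also applied to the ecology indices.
- **Abundance:** after a log-ratio transformation at each taxonomic level, "Then the transformed relative abundance of each individual taxa at multiple time points will be fitted by the linear mixed model".
- **Composition of the whole community:** "We will utilize skyline plots to visualize the patterns of community structure in terms of relative abundances in the collected samples", with rank-abundance plots and heat-maps beside them.

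Section 9.1 mentions clustering and phylogenetic analyses, and lists community dissimilarities among the contributors to overall diversity. It gives no distance measure and no comparison over time. Neither section states how the many taxon-level results will be adjusted or read together.

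On numbers, Section 12.2 says "We plan to accrue 20 patients over 2 years". Section 9.1 describes a "stool sample for microbiome analysis at baseline, end of completion and 3-6 month follow up (last stool sample is optional"). The number of complete stool pairs is not projected.

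**The concern.** Composition is the one component of Hypothesis 3 with no analysis aimed at it as a whole. Alpha diversity describes each sample on its own and can stay level while the taxa present turn over. The taxon models do bear on composition, but they return one result per taxon and per level, with no rule for turning the set into one statement. The plots carry no error rate.

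At stake is how well a sentence such as 'composition changed after radiation' could be supported. As the plan stands it would rest on visual judgement or on a list of taxa. Small changes spread over many taxa are weak one at a time but add up when the community is compared as a unit, so this is where a taxon-by-taxon analysis loses most.

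**Working it through.** **The plan's own figure.** There is none to reproduce. The documents give no alpha, power, effect size, SD, number of taxa or multiplicity rule for the microbiome aim. All inputs below except the 20 patients are assumptions.

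**Step 1: unadjusted taxon tests with no true change.** Expected false positives = taxa x 0.05. For 150 taxa this is 150 x 0.05 = 7.5, and simulation gives about 7.3 to 7.5. The chance of at least one, for independent taxa, is 1 - 0.95^m: 92% for m = 50 and 99% for m = 100.

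**Step 2: power for a single taxon.** For a paired t-test with 20 pairs and a shift of d SDs of the paired difference:

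- d = 0.3: 25% unadjusted, 1% at a Bonferroni level for 100 taxa.
- d = 0.5: 57% and 6%.
- d = 0.8: 92% and 32%.

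**Step 3: a shift in some of the taxa.** Assumptions: 150 taxa on a centred log-ratio scale, within-patient SD 1 per sample, between-patient SD 1.5, and taxa either independent or in blocks of 10 with correlation 0.3. The community test is a paired permutation test on Euclidean (Aitchison) distance. The comparator is at least one taxon significant after Benjamini-Hochberg.

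| Pairs | Shift | Taxa shifted | Community test | Any taxon |
|---|---|---|---|---|
| 20 | 0 | none | 4-8% | 3-6% |
| 20 | 0.25 | 40 | 25-32% | 11-12% |
| 20 | 0.35 | 40 | 56-75% | 17-22% |
| 20 | 0.5 | 40 | 98-100% | 45-47% |
| 20 | 0.7 | 40 | at least as at 0.5 | 90-93% |
| 20 | 0.5 | all 150 | at least as with 40 | 93-96% |
| 12 | 0.35 | 40 | 30-39% | about 11% |
| 12 | 0.5 | 40 | 71-90% | 13-21% |

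**Step 4: a shift in every taxon.** Here d is in SDs of the paired difference, with 50 or 100 taxa, independent or correlated. The scales convert by the square root of 2: a Step 3 shift of 0.35 is 0.35 / 1.41 = 0.25 on this scale.

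- 20 pairs: d = 0.1, community 9-34% and any taxon 8-11%; d = 0.2, 53-99.5% and 27-32%; d = 0.3, 99-100% and 60-73%; d = 0.5 or more, both about 100%.
- 12 pairs: d = 0.2, 27-84% and 12-18%; d = 0.3, 73-100% and 27-32%; d = 0.5, 100% and 80-90%.

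Both sets of assumptions agree. The community test is clearly ahead for small diffuse shifts, the gap closes as shifts grow, and at the smallest shifts both approaches mostly fail.

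**The case against.** The strongest reply is that the aim is exploratory and worded as description, no decision or sample size depends on it, and plots with taxon models are a reasonable way to describe change. That stands, and it is why the priority is low. It does not remove the gap: Hypothesis 3 still makes a prediction about composition, and the plan formally analyses the other two components.

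A second reply is that the log-ratio models by taxon and by level are themselves a formal analysis of composition, and that Section 9.1 shows between-sample structure was considered. This also stands in part. It would be wrong to say composition gets nothing but plots. What is missing is an analysis of the community as a unit over time.

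Third, a reader might infer that a broad shift would probably be missed. The documents do not support that. They give no effect size or taxon count, and the low detection figures assume false-discovery control that the plan does not state. At 20 pairs the adjusted taxon models make a discovery in 90-93% of trials for a 0.7 shift in 40 taxa, and in 93-96% if all 150 shift by 0.5. Read unadjusted, 40 taxa shifted by 0.5 give about 18 significant results against 7.5 under no change. For independent taxa the null SD is sqrt(150 x 0.05 x 0.95) = 2.7, so that excess of 10.5, about 3.9 SDs, would be noticed. It would be harder to judge with smaller shifts or correlated taxa, and the plan gives no rule for judging it.

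Finally, 20 complete pairs is optimistic when the last stool sample is optional. That lowers the power of the proposed test too.

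**Conclusion.** The point holds in limited form. Section 12.3 has no community-level test of composition over time and no multiplicity rule for its taxon models. Two consequences follow, depending on a choice the plan leaves open. With adjustment, a small diffuse shift could go undetected. Without it, about 7 of 150 taxa would be significant by chance, and a scattered list could not confirm a change.

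The size rests on assumptions. With 20 pairs and 40 of 150 taxa shifted by 0.35, detection is about 56-75% for a paired community test against 17-22% for any adjusted taxon; with 12 pairs, about 30-39% against 11%. The stronger statement, that a broad change would be missed, is not established: at 20 pairs, larger shifts would be found by the planned taxon models. This is a worthwhile improvement to an exploratory aim, with no bearing on the primary safety conclusion.

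**What to change.** Add one paragraph to the microbiome part of Section 12.3:

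- One prespecified exploratory test of composition: PERMANOVA on Aitchison distance (Euclidean distance on centred log-ratios, consistent with the planned log-ratio transformation), at a stated taxonomic level and with a stated rule for zero counts.
- Permutations restricted within patient. This matters: under the Step 3 assumptions an unrestricted permutation test detected 0%, because differences between patients swamp the within-patient change. The plan proposes no such test; the figure only guides how the new one should be specified.
- Baseline versus end of radiation as the main contrast. Baseline versus 3-6 months is the second, with fewer pairs expected, each using patients who have both samples and reporting how many.
- A dispersion check, so that a change in spread is not read as a change in location.
- The statement on composition based on this test. The plots and the taxon models, the latter with false-discovery control, kept as description of where any change lies.

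The cost is a paragraph and a few lines of code in vegan, which Section 12.3 already names. No new samples are needed. The downside is two more exploratory p-values. Accrual is closed, but Section 9.1 defers the 16S analysis until all samples are in, so the test can still be prespecified if the sequence data have not been examined; otherwise it should be labelled post hoc.
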